### 10.2.9 Length of ICU Stay

Length of ICU will be compared using a Van Elteren test.

The effect of randomised treatment will be estimated by the shift in location using the Hodges-Lehmann estimator and will be presented together with its associated 95% confidence interval.

It is expected that a substantial proportion will have died in ICU. Therefore, to take account of ICU mortality, a competing risk analysis will be performed for time to ICU discharge, considering ICU death as a competing risk. Cumulative incidence functions (CIF) will be calculated and presented together with their associated 95% confidence interval. Comparison of the curves will be done using Gray's test. The median time to discharge will be estimated for both randomised groups.

In addition, stacked CIF curves will be presented for both randomised groups of time to ICU discharge and time to ICU death.

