## 5 Sample Size Determination

Based on the results of a pilot study at Stanford University in which the standard deviation of the percentage  $ADC < 0.650 \text{ mm}^2/\text{s}$  in comparable post-CA patients was 8.9%, it was estimated that 56 patients would be necessary in each study group to show a 40% reduction in the extent of cerebral ischemia with a power of 80% at a two-sided alpha level of 0.05.

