#### **7.7 Multiple Comparisons**

This study has only one primary endpoint, so no multiplicity issues are present.

For the secondary endpoints, no adjustment will be made to the significance level to account for multiple testing.

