### 10.2.2 CPC 3-5 at 180 Days

The %patients with CPC 3-5 at Day 180 will be analysed using the same methodology as used for the analysis of the CPC scores at discharge (see section 10.2.1) whereby all patients who did not have CPC scores due to death are given a score of 5.

A sensitivity analysis will be performed whereby all patients who did not die and do not have CPC data will be given a score of 5.

### 10.2.3 SF-36 Questionnaire at Day 180

Of main interest is the total score obtained from the SF-36 questionnaire. In addition, the subscales will be analysed using the same methodology.

It should be kept in mind that a considerable proportion of patients will have died prior to Day 180 and that therefore, the SF-36 results in these patients are not defined. A comparison of the scores in the survivors will yield biased estimates of the treatment effect, since the element of randomisation is lost in such comparison if survival depends on the assigned treatment group.

Therefore, the effect of randomised group will be evaluated by the "survivor average causal effect" (SACE), defined as the effect of randomised treatment on the outcome among the subgroup of patients that would have survived under either treatment arm. The SACE will be calculated as explained by Hayden et al by weighing the result of each survivor by the estimated survival probability in the other group. The confidence interval will be obtained by bootstrapping (500 samples).

The estimated survival probabilities will be obtained from a logistic regression using survival as dependent variable and the baseline covariates given in Section 7.4 as independent variables.

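### ICU stay is compared by two tests with no stated ranking, and its only between-arm effect with a confidence interval does not account for ICU death

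*SAP*

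**What the plan says.** SAP 10.2.9 gives length of ICU stay two comparisons. The first: "Length of ICU will be compared using a Van Elteren test", with the treatment effect estimated by the Hodges-Lehmann shift and its 95% CI. The second follows from a warning: "It is expected that a substantial proportion will have died in ICU". The SAP continues: "Therefore, to take account of ICU mortality, a competing risk analysis will be performed for time to ICU discharge", with ICU death as the competing event. This analysis yields cumulative incidence curves with CIs, a median time to discharge per arm and a test: "Comparison of the curves will be done using Gray's test".

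Neither analysis is called main, supportive or sensitivity, although the SAP uses the label sensitivity analysis for CPC at day 180 (10.2.2) and for tracheostomy (10.2.11). Section 10.2.9 does not say whether or how patients who die in ICU enter the Van Elteren test.

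Three other places bear on this:
- SAP 7.3 promises an effect estimate with 95% CI for every secondary variable and says all group comparisons should account for shockable rhythm.
- SAP 7.7: "For the secondary endpoints, no adjustment will be made to the significance level to account for multiple testing".
- Protocol 6.9.3 gives the Van Elteren test for clearly non-normal continuous secondary endpoints. It mentions no competing-risk analysis and has no rule for two tests of one endpoint.

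**The concern.** The two tests answer different questions. The Van Elteren test asks whether stays are longer or shorter. Gray's test asks whether patients leave the ICU alive sooner and more often. If treatment changes ICU mortality, the first answer is hard to interpret, and the SAP's own sentence on expected deaths shows that its authors saw this. Yet the analysis added for that reason supplies only curves, a p-value and a median per arm. The between-arm effect promised in SAP 7.3 comes solely from the analysis that does not account for death.

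At stake is what the report says about ICU stay. With no ranking, the conclusion can follow whichever test is quoted. The reported effect can show a survival benefit as a longer stay, or miss it.

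**Working it through.** **No plan figure to reproduce.** The documents give no power, error rate, mortality figure or stay distribution for ICU stay. The sample size in SAP 5 concerns the primary endpoint only.

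**1. The two ways of handling deaths.**
- Deaths included by raw stay: a patient who dies early has a short stay and ranks beside patients discharged early.
- Deaths excluded: the comparison is among ICU survivors. For SF-36, SAP 10.2.3 says of this kind of comparison: "A comparison of the scores in the survivors will yield biased estimates of the treatment effect, since the element of randomisation is lost".

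**2. Inputs (all but the arm size are assumptions).**
- Arm size: 112 planned less the 3 exclusions in SAP 6.2 is 109, about 55 per arm.
- ICU death 50% v 35%. Protocol 4.1 implies that about 45–50% survive (40% without major impairment, plus 5–10% with it). The 15-point benefit is an assumption.
- Lognormal stays, log-SD 0.6, no censoring, unstratified tests, two-sided 5%. The 5% is inferred from SAP 5 ("with a power of 80% at a two-sided alpha level of 0.05") and the 95% CIs; 10.2.9 states no level.
- Median days to death/discharge alive: 4/10, 5/8, 8/8, 10/8.

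**3. Direction of the rank test with all deaths included.** Let θ be the chance that a discharge time exceeds a death time: θ = Φ(ln(m_discharge/m_death)/(0.6√2)). With ICU mortality p0 (control) and p1 (intervention), the chance that an intervention stay exceeds a control stay is

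½ + (p0 − p1)(θ − ½).

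The rank statistic then has mean z ≈ (p0 − p1)(θ − ½)/√((2n+1)/(12n²)). With n = 55 the denominator is √(111/36300) = 0.0553. The chance of a significantly longer stay is 1 − Φ(1.96 − z). At 4/10, θ = Φ(0.916/0.849) = 0.860, z = 0.15 × 0.360/0.0553 = 0.98, and the chance is 16%.

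The last two columns come from simulation, 3,000–4,000 trials per scenario:

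| Median death/discharge day | θ | Mean z | Significantly longer, formula | Significantly longer, simulated | Both significant, opposite directions |
|---|---|---|---|---|---|
| 4/10 | 0.860 | 0.98 | 16% | 16% | 10% |
| 5/8 | 0.710 | 0.57 | 8% | 8% | 4% |
| 8/8 | 0.500 | 0 | 2.5% | 3% | 0.5% |
| 10/8 | 0.396 | −0.28 | 1.3% | 1% | 0% |

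**4. Gray's test, same scenarios.** Simulated: favourable in about 33–37%. As a rough check from the eventual proportions discharged alive, 0.15/√(0.25/55 + 0.2275/55) = 0.15/0.0932 = 1.61, and 1 − Φ(1.96 − 1.61) = 36%.

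**5. Opposite signs.** Van Elteren and Gray point in opposite directions in 84% (4/10) and 72% (5/8) of benefit trials. With no effect they already do so in 68% and 57%. The excess is 84 − 68 = 16 and 72 − 57 = 15 points.

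**6. Deaths excluded.** With ICU mortality 50% v 30% and the same stay distribution for survivors in both arms, the survivors-only test has mean z near 0 and rejects in about 5% of trials, while Gray's test rejects in about 55%. The benefit is missed rather than reversed.

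**7. No effect.** If either test may be read as the result, independence gives 1 − 0.95² = 9.75%. Simulation gives about 9–10% in most timings, and about 8% at 4/10.

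**The case against.** Both analyses are prespecified, and the SAP requires stacked curves for ICU discharge and ICU death (10.2.9), counts of ICU deaths and discharges by arm (8.1), and CPC 3–5 with death scored 5 (10.2.1). A longer stay caused by better survival would be visible to a careful reader. The Van Elteren test is listed first and is the protocol's method, so Gray's test could be taken as supportive. SAP 7.7 openly leaves secondary endpoints unadjusted.

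Much of this stands, and it rules out three stronger readings that a reader might infer:

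- **That the tests would usually contradict each other under a benefit.** The 84% rate of opposite signs has a no-effect baseline of 68%, and most of it is non-significant noise. Significant contradiction occurs in 0–10% of trials. The 10% needs a median death at day 4, which is hard to square with protocol 6.7, where full ICU treatment continues to at least day 5 with narrow exceptions.
- **That the Van Elteren test would report a benefit as a cost.** This needs deaths to be counted and to come earlier than discharges. The SAP states neither, and never calls a longer stay worse.
- **That the trial's error rate is inflated.** The 9–10% concerns one secondary endpoint under a declared no-adjustment policy.

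The objection does not close the gap in 10.2.9. Reading Gray's test as supportive would make the test that does not account for death decisive, against the SAP's own reasoning. The extra displays supply no between-arm effect with a CI.

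**Conclusion.** The point holds as a gap in the ranking and estimation of one secondary endpoint, and it should be corrected. Three facts rest on the text alone: the two tests are unranked, the handling of ICU deaths in the Van Elteren test is unstated, and the only between-arm effect with a 95% CI is the Hodges-Lehmann shift, which does not account for death under either handling.

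The size rests on assumed mortality and timings. For a fall in ICU death from 50% to 35%, the rank test is significantly longer in 1–16% of trials and significantly contradicts Gray's test in 0–10%. Where deaths come as late as discharges, or are excluded, the rank test tends to miss the benefit instead. The primary endpoint and its alpha are unaffected.

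**What to change.** Before unblinding, amend SAP 10.2.9 to:

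1. Name the competing-risk comparison of time to ICU discharge alive as the analysis on which the ICU-stay conclusion rests.
2. Stratify Gray's test by shockable rhythm, in line with SAP 7.3; at present 10.2.9 does not say that it is stratified.
3. Report a between-arm effect with 95% CI: the difference in cumulative incidence of discharge alive at one fixed, prespecified day, or a subdistribution hazard ratio.
4. Keep raw ICU stay as supportive or descriptive, shown separately for patients discharged alive and patients who died in ICU. If the Van Elteren test is kept as supportive, state how deaths enter it.
5. Document the departure from the Van Elteren method of protocol 6.9.3, as protocol 6.10 requires.

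The cost is SAP wording and a little more analysis work for the effect estimate and the stratified test; both comparisons are already planned. The downside is that the raw-stay p-value is lost or demoted. If unblinding has already taken place, the ranking should be reported as decided afterwards.

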### **7.3 Statistical Comparisons between Groups**

Since randomization was stratified by the presence of shockable rhythm, all comparisons between groups should account for this stratification.

So, an ANOVA using factors for randomized group and shockable rhythm will be used rather than a two-sample t-test for the comparison of continuous and normally distributed variables. Continuous variables showing serious deviations from normality will be compared using a Van Elteren test. This test will also be used for the comparison of ordinal data.

For binary and categorical data, a Cochran-Mantel-Haenszel test will be used.

For primary and secondary variables, the effect of treatment will be estimated by an appropriate statistic and presented together with its associated 95% confidence interval.

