#### 10.2.10 Duration of Mechanical Ventilation

The duration of mechanical ventilation will be analysed using a Van Elteren test.

The effect of randomised treatment will be estimated by the shift in location using the Hodges-Lehmann estimator and will be presented together with its associated 95% confidence interval.

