#### 10.2.11 Placement of Tracheostomy

The %patients with tracheostomy will be analysed using a Cochran-Mantel-Haenszel test with shockable rhythm as stratification factor.

The effect of randomised group will be estimated by the stratified odds ratio between the two groups and presented along with its 95% confidence interval.

A sensitivity analysis will be performed whereby patients with missing data will be imputed according to a worst-case scenario and will be assumed to have had a tracheostomy.

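### SAP 10.2.9 names Gray's test without the shockable-rhythm stratum, and 10.2.9 and 10.2.10 pair a stratified Van Elteren test with an interval that, in its usual form, is pooled

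*SAP*

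**What the plan says.** SAP 7.3 sets the general rule. Because randomisation was stratified by shockable rhythm, "all comparisons between groups should account for this stratification". For skewed variables it adds: "Continuous variables showing serious deviations from normality will be compared using a Van Elteren test". For estimates it asks only that "the effect of treatment will be estimated by an appropriate statistic and presented together with its associated 95% confidence interval".

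SAP 10.2.9 gives ICU stay two analyses. The first is a rank comparison: "Length of ICU will be compared using a Van Elteren test", with a Hodges-Lehmann shift and 95% interval. The second is a competing-risk analysis of time to ICU discharge, added because many patients are expected to die in the ICU: "Comparison of the curves will be done using Gray's test". No stratum is named for the shift or for Gray's test.

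SAP 10.2.10 repeats the pairing for ventilation: "The duration of mechanical ventilation will be analysed using a Van Elteren test", with the effect "estimated by the shift in location using the Hodges-Lehmann estimator".

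Elsewhere rhythm is written in. SAP 10.2.1 and 10.2.11 use a "Cochran-Mantel-Haenszel test with shockable rhythm as stratification factor" with a stratified odds ratio, and the longitudinal model in SAP 10.2.5 has a rhythm term. The statistical section of the protocol (6.9.3) plans a stratified log-rank test for censored outcomes and a Van Elteren test stratified by rhythm for skewed ones.

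**The concern.** Gray's test and the Hodges-Lehmann shift are both pooled in their usual form. A programmer who works from 10.2.9 alone would run them that way.

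For Gray's test, allocation is balanced within rhythm strata. If rhythm predicts discharge alive, a pooled test counts the between-stratum variation as noise although the design has already removed it from the treatment contrast. The test becomes conservative and loses power. This matters somewhat because it is the only ICU-stay analysis in the SAP that takes account of ICU deaths.

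For the shift, the usual interval is the set of shifts that a pooled Wilcoxon test does not reject. The p-value beside it comes from Van Elteren, which ranks within strata. The two can fall on opposite sides of 0.05, and the report would then show a significant p-value with an interval that covers zero, or the reverse.

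**Working it through.** **Figures in the plan.** Neither document gives a power figure for ICU stay or ventilation. The only sample-size figure is for the MRI endpoint: 56 per group, SD 8.9, 80% power, two-sided 0.05. It implies a detectable difference of 8.9 × (1.960 + 0.842) × √(2/56) = 4.71 points, so a control mean of 4.71/0.40 = 11.8%, which is not stated. That has no bearing on ICU stay, so the size of this point has to come from simulation.

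**Inputs from the documents.** N = 112, 1:1, balanced within rhythm. Protocol 4.1 gives 40% good survival plus 5 to 10% impaired, so about 45 to 50% alive, which anchors the share discharged alive.

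**Assumed, because not given.** The shockable share, the rhythm effect on discharge and on stay, and the treatment effect. I took 60% shockable (varied from 50 to 70%) and kept overall control-arm discharge near 50%. For example, 0.6 × 65% + 0.4 × 25% = 49% for a moderate effect, and 0.6 × 75% + 0.4 × 12% = 49.8% for a strong one. The main subdistribution hazard ratio was 2.1. That is a large effect (50% discharged becomes 1 − 0.5^2.1 = 77%), chosen to put power in a readable range.

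**Gray's test.** With no censoring it was computed as a log-rank test in which ICU deaths stay in the risk set:
- pooled: Z = Σ(O − E) / √ΣV over all patients
- stratified: Z = Σ_h(O_h − E_h) / √Σ_h V_h, with risk sets formed within rhythm stratum h

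Results from 4,000 trials per row:

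| Rhythm effect (discharged alive, shockable v not) | Hazard ratio | Pooled rejects | Stratified rejects | Verdicts differ |
|---|---|---|---|---|
| none (50 v 50%) | 1 | 4.6% | 4.6% | 0.5% |
| moderate (65 v 25%) | 1 | 3.5% | 5.3% | 2.0% |
| strong (75 v 12%) | 1 | 1.6% | 5.3% | 3.8% |
| none (50 v 50%) | 2.1 | 87.1% | 86.6% | 1.2% |
| mild (55 v 42%) | 2.1 | 86.2% | 86.8% | 2.3% |
| moderate (65 v 25%) | 2.1 | 77.9% | 85.8% | 9.0% |
| moderate, 70% shockable (60 v 20%) | 2.1 | 78.4% | 85.4% | 7.8% |
| moderate, 50% shockable (70 v 30%) | 2.1 | 76.0% | 85.4% | 10.6% |
| moderate (65 v 25%) | 1.5 | 28.6% | 36.0% | 8.5% |
| strong (75 v 12%) | 2.1 | 54.1% | 84.7% | 30.7% |

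The moderate rows lose 7.9, 7.0, 9.4 and 7.4 points. The strong row loses 30.6. Separate runs with 65% v 20% gave type I error of 2.6% pooled and 5.2% stratified, and power of 43% v 51% and 62% v 71%. A further set with 65% v 20 to 25% lost about 10 to 12 points. Hence the range of roughly 7 to 12 for a moderate effect. If rhythm does not matter, stratifying costs 87.1 − 86.6 = 0.5 points, which is within simulation error.

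**Hodges-Lehmann interval against Van Elteren.** With W_h the treated rank sum in stratum h (m_h treated of n_h), Van Elteren sums [W_h − m_h(n_h + 1)/2] / (n_h + 1) over strata and divides by its standard error. The ordinary Hodges-Lehmann interval excludes zero essentially when the pooled Wilcoxon test rejects, so the two tests were compared. Durations were log-normal with log-SD 0.9, and the treatment shift was 0.5 on the log scale.

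| Rhythm shift (log units) | Pooled interval excludes 0 | Van Elteren rejects | Disagree |
|---|---|---|---|
| 0 | 81.6% | 81.2% | 2.3% |
| 0.2 | 81.2% | 81.0% | 2.3% |
| 0.4 | 78.5% | 79.0% | 2.6% |
| 0.9 | 73.0% | 80.2% | 8.0% |

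With a treatment shift of 0.3 and a rhythm shift of 0.4, 4.2% disagreed. With no treatment effect, 0.9 to 2.3% disagreed. What drives this is the rhythm shift relative to the within-stratum SD. With a rhythm shift of 0.8 and a treatment effect of 0.5 SD, disagreement was 21%, 15%, 11% and 7% at log-SD 0.5, 0.6, 0.7 and 0.9. The top figure needs a between-rhythm gap of 0.8/0.5 = 1.6 SD.

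**The case against.** The best defence is that the SAP is silent, not wrong. SAP 7.3 covers all between-group comparisons, and a general section governs the endpoint sections. Sections 10.2.9 and 10.2.10 name no stratum for Van Elteren either, yet nobody doubts that rhythm is meant. Where the authors intend to drop a stratification factor they say so, as SAP 7.6 does for site. No section drops rhythm.

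Much of this stands. A reader might infer that the SAP breaks its own rule by prescribing an unstratified Gray's test. The text does not support that, because the word unstratified appears nowhere. What remains is that Van Elteren is stratified by construction while Gray's test is not, so silence has different consequences for the two. Other sections spell rhythm out and this one does not. Two programmers could produce two p-values, with different verdicts in about 8 to 11% of simulated trials under a moderate rhythm effect.

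A reader might also infer that the Hodges-Lehmann shift breaches 7.3. It does not: the stratification rule is about comparisons, and estimates need only an appropriate statistic. This limb is a mismatch between test and interval.

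Finally, these are secondary endpoints without multiplicity control (SAP 7.7), and the primary ANOVA already includes rhythm. Both facts are correct and keep the point minor.

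**Conclusion.** The point holds as an ambiguity worth closing, with minor severity. If Gray's test is run pooled, the competing-risk comparison of ICU discharge is conservative. It loses about 0 to 1 point of power with a weak rhythm effect, roughly 7 to 12 with a moderate one, and about 31 in the extreme setting. These figures rest on an assumed shockable share, rhythm effect and treatment effect, none of which the documents give. Type I error is not inflated.

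It would be too strong to say that power is lost for ICU stay as a whole. The first-listed test of stay, and the only test of ventilation, is Van Elteren, which is already stratified and loses nothing.

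The disagreement between p-value and interval is real but usually uncommon: about 2 to 8% of simulated trials in most settings. Values of 15 to 21% belong to a strong rhythm effect relative to the within-stratum SD and should not be read as typical.

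**What to change.** In SAP 10.2.9, state that Gray's test is stratified by shockable rhythm. The cumulative incidence curves can still be shown by arm.

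In SAP 10.2.9 and 10.2.10, report a rhythm-stratified location shift, with the 95% interval formed by inverting the Van Elteren test (the shifts that it does not reject at 0.05). An aligned Hodges-Lehmann interval would not fully do this: it inverts the aligned-rank test, which still disagreed with Van Elteren in 2 to 3% of simulated trials. If the sponsor prefers the ordinary interval, the SAP should label it descriptive and say that it is pooled over rhythm.

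The cost is one clause and one strata option for Gray's test, plus revised wording in two sections and a few lines of code for the interval. The simulations show no material loss from stratifying when rhythm turns out not to matter.

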#### 10.2.10 Duration of Mechanical Ventilation

The duration of mechanical ventilation will be analysed using a Van Elteren test.

The effect of randomised treatment will be estimated by the shift in location using the Hodges-Lehmann estimator and will be presented together with its associated 95% confidence interval.

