Censored outcomes will be presented using Kaplan-Meier curves analyzed using a stratified long-rank test. The treatment effect will be expressed as a hazard ratio.

Prespecified subgroup analysis

Prespecified subgroup analysis will be performed for the primary endpoint according to age (> or <65 years), gender, time-to-ROSC (> or < 25 min), Initial rhythm (shockable or non-shockable), presence of bystander CPR (yes/no), presence of chronic hypertension (yes/no) and treatment center.

The interaction will be assessed using an analysis of variance.

The full statistical methods planned for this trial will be written as a separate document (Statistical Analysis Plan) prior to the completion of the study.

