#### **7.4 Methods for Withdrawals, Missing Data and Outliers**

For the primary endpoint, multiple imputation methodology will be used to account for missing data. A total of 100 imputations will be done. The imputation model will include the following:

Age, gender, presence of bystander CPR, presence of initial shockable rhythm, neuron specific enolase at days 1-2-3-4-5, presence of a malign EEG pattern on Day 1 and allocated treatment and death within 7 days of randomisation.

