### 10.2 Secondary Endpoints

The statistical analysis of all secondary endpoints will be performed for the FAS and PPS.

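### Duration of mechanical ventilation is compared by a rank test alone, without the competing-risk analysis that the SAP adds to the same test for ICU stay because of expected deaths

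*SAP*

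**What the plan says.** SAP 10.2.10 has two sentences. The first is "The duration of mechanical ventilation will be analysed using a Van Elteren test"; the second reports a Hodges-Lehmann shift with its 95% confidence interval. SAP 10.2 sets the population: "The statistical analysis of all secondary endpoints will be performed for the FAS and PPS". Patients who die on the ventilator are therefore in the analysis set, but no sentence says what value they contribute.

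SAP 10.2.9 gives length of ICU stay the same test and estimator. It then says "It is expected that a substantial proportion will have died in ICU", and for that reason "to take account of ICU mortality, a competing risk analysis will be performed for time to ICU discharge", with cumulative incidence functions, 95% confidence intervals and Gray's test. It also promises that "stacked CIF curves will be presented for both randomised groups of time to ICU discharge and time to ICU death". Section 10.2.10 does not refer back to any of this.

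Protocol 6.5.3 expects every patient to be intubated and ventilated. Protocol 6.8.1 lists length of mechanical ventilation among the items recorded at ICU discharge and does not define it further.

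**The concern.** The reason given in 10.2.9 for going beyond the rank test applies equally to ventilation: the patients who die in ICU are largely patients who were being ventilated. Time on the ventilator ends in two opposite ways, liberation or death, and a single duration does not tell them apart. An arm with more early deaths accumulates fewer ventilated days, and a shift in its favour could be reported as a benefit. Conversely, an arm with quicker liberation and fewer deaths could show no shift at all. In an open-label trial of a haemodynamic strategy with survival-dependent outcomes, readers are likely to take shorter ventilation as recovery.

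**Working it through.** **1. Does any other section cover death on the ventilator?**

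- SAP 7.3 only assigns tests to types of variable.
- SAP 7.4 is confined to the primary outcome: "For the primary endpoint, multiple imputation methodology will be used to account for missing data".
- Protocol 6.9.3 has a general line, "Censored outcomes will be presented using Kaplan-Meier curves analyzed using a stratified long-rank test". It names no endpoint and does not treat death as a competing event.
- SAP 10.2.3 recognises the problem for SF-36 scores, where a survivor comparison is called biased "since the element of randomisation is lost in such comparison if survival depends on the assigned treatment group". Its survivor average causal effect is carried over to the Wechsler score, ADL and walking distance, but not to ventilation.

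The documents state no figure for this endpoint, so there is none to reproduce.

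**2. How common will death be?** Protocol 4.1 gives 40% surviving without major impairment and a further 5-10% surviving with it. Implied mortality is 100 - 40 - 10 = 50% to 100 - 40 - 5 = 55%. This supports centring the illustration near 50%. The documents give no mortality difference between arms, no timing of deaths and no ventilation times; those inputs are assumptions.

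**3. Illustration with no true difference in survivors.** Inputs: 56 per arm (SAP 5). Survivor ventilation time is lognormal with log-SD 0.6 and median 4.5 days, identical in both arms. Early deaths are uniform on days 0.3-3, late deaths uniform on days 5-9, and death ends ventilation. An unstratified rank-sum test stands in for the Van Elteren test. There are at least 3,000 simulated trials per row.

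| Mortality, arm 1 v arm 2 | Excess deaths | Mean Hodges-Lehmann shift (days) | Significantly shorter in arm 1 |
|---|---|---|---|
| 50% v 50% | none | +0.01 | 2.5% |
| 60% v 40% | all early | -0.74 | 28% |
| 55% v 45% | all early | -0.36 | 10% |
| 60% v 40% | mixed early and late | -0.15 | 4.5% |
| 55% v 45% | mixed early and late | -0.07 | 3.0% |

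Repeat runs of the second row gave 26-29%. A Van Elteren test with two assumed rhythm strata gave 27% there and 10% at 55% v 45%. With a 7-day survivor median the effect is larger: 43% at 60% v 40% all early, and 14% when mixed.

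**4. Dependence on the rule for deaths.** In the 60% v 40% all-early case, giving deaths the worst rank turns the result round: significantly longer in arm 1 in about half of trials (48-51%). The same data can thus point either way.

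**5. What a competing-risk analysis would show.** Take constant daily hazards (assumed): liberation 0.15 v 0.10 and death on the ventilator 0.05 v 0.10. The total hazard is 0.15 + 0.05 = 0.20 in one arm and 0.10 + 0.10 = 0.20 in the other, so total ventilated time has the same distribution in both. The rank test on that time rejects in 4.4% of trials (two-sided 5%). Yet the proportion ending ventilation alive is 0.15/0.20 = 75% v 0.10/0.20 = 50%. Cumulative incidence functions display that difference; the planned analysis cannot.

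**The case against.** Four points on the other side carry weight.

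First, observed ventilated days are well defined for a patient who dies. If one arm has more early deaths, its patients do spend fewer days ventilated, and a rank test that detects this is not in error. A reader might infer that the planned test is invalid or that its type I error is inflated. The documents do not support that, since they never say the endpoint means liberation. The percentages above measure how often the result would mislead if read as faster liberation.

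Second, the largest figure needs a 20-point mortality gap with every excess death in the first three days. Protocol 6.7 calls for full ICU treatment for at least 5 days, with two exceptions for earlier discontinuation, so that case is an upper bound and not a forecast for this trial.

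Third, one might infer that late deaths would make ventilation look longer. In the illustration that appears with a 4.5-day median (+0.45 day at 60% v 40%), vanishes with a 7-day median (0.00) and becomes -0.05 if patients may be liberated before dying. It is not a dependable effect. Nor does the illustration show bias in a survivors-only comparison: survivor times are identical by construction, and its rejection rate stays nominal. The caution about survivors rests on the SAP's own reasoning for SF-36.

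Fourth, an imbalance in deaths would not be hidden. SAP 8.1 tabulates deaths by arm, and SAP 10.2.9 plots ICU discharge and ICU death. These warn the reader, but ICU discharge is a different event from the end of ventilation, so they do not supply the split for this endpoint.

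**Conclusion.** The point holds as a cheap improvement of low priority. The SAP's own reason for a competing-risk analysis of ICU stay applies to ventilation, and no other section covers death on the ventilator. Unless mortality is equal, the planned comparison cannot be interpreted as faster liberation, and its direction depends on how deaths are entered. With assumed inputs, the chance of a misleading shorter result runs from the nominal 2.5% (equal mortality), through about 4% (60% v 40%, mixed timing) and about 10% (55% v 45%, early excess), to about 26-28% (60% v 40%, all early), for a 4.5-day survivor median. The endpoint is one of many secondary ones. Nothing here touches the primary analysis or the sample size.

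**What to change.** In SAP 10.2.10:

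1. Add the analysis already specified in 10.2.9, applied to time to end of mechanical ventilation alive, with death on the ventilator as the competing event: cumulative incidence functions with 95% confidence intervals by arm, and Gray's test.
2. Where the collected data allow, class ventilation that ended through withdrawal of therapy and was followed by death with the competing event. This can matter: in an assumed late-death case (60% v 40%), the day-7 incidence of ending ventilation alive is 31% v 46% with this classing, but 56% v 61% if the late deaths are counted as ended alive.
3. Keep the Van Elteren and Hodges-Lehmann analysis on observed ventilated time up to death, label it as time spent ventilated, and interpret it together with the competing-risk result.

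The cost is a few lines of SAP text and a little more analysis with a method already planned. It also needs a check that existing data show how ventilation ended. The case report form is not in the documents, and SAP 4.2 indicates that all patients had already been included, so new collection may not be possible. If the reason for ending is unavailable, step 2 should be dropped and the limitation stated.
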